1. INTRODUCTION

This protocol describes a 6-month, open label extension study (A1281201) of the A1281198 study. The purpose of adding this extension study to the ongoing Geodon pediatric bipolar program is to obtain additional longer term safety data in children and adolescents with Bipolar I disorder treated with ziprasidone.

Studies A1281198 and A1281201 are being conducted to fulfill a Pediatric Research Equity Act (PREA) commitment to assess the safety and effectiveness of Geodon® (ziprasidone) as a treatment for bipolar disorder in pediatric patients 10 to 17 years of age, which was issued by the United States (US) Food and Drug Administration (FDA) to Pfizer in August 2004.

1.1. Mechanism of Action/Indication

Ziprasidone is an atypical antipsychotic with a high affinity for the dopamine D2 receptor and the 5-Hydroxytryptamine Receptor 2A (5-HT2A) receptors. It blocks re-uptake of serotonin and norepinephrine and exhibits 5-Hydroxytryptamine Receptor 1A (5-HT1A) agonist activity. The indication for this study is pediatric Bipolar I Disorder. The study will include out-patient and/or inpatient, male and female subjects aged 10-17 (inclusive) who meet the Diagnostic and Statistical Manual of Mental Disorders Fifth Edition (DSM V) diagnostic criteria for Bipolar I Disorder (current or most recent episode manic) and who participated in Study A1281198.

1.2. Background and Rationale

Bipolar I Disorder is a lifelong disease that is potentially debilitating to the patient and presents serious complications within the patient's family structure. Over half of all bipolar patients report that their symptoms first emerged during childhood or adolescence, and onset before adulthood is associated with greater social morbidity.¹ Children and adolescents with mania often show markedly labile mood, with a mixed or dysphoric picture and intense irritability, as well as severe psychosocial impairment.^{2,3} The costs to society and the public health system are immense. Recognizing the onset of these disorders in children or adolescents is a critical health concern and initiating treatment as early as possible is vital to maximize the probability of a positive outcome for the patient.

Bipolar disorder can be reliably diagnosed in children and adolescents aged 10-17 years, using the same criteria used for adults as outlined in the Diagnostic and Statistical Manual of Mental Disorders Fifth Edition (DSM V), and supported by structured diagnostic interviews such as Kiddie Schedule for Affective Disorders and Schizophrenia (K-SADS), as affirmed by the American Academy of Child and Adolescent Psychiatry (AACAP) guidelines.⁴ Existing data support the diagnostic and therapeutic continuity between adult and pediatric bipolar disorder. For adults with acute mania in the setting of bipolar disorder, the efficacy and safety of a variety of medications has been established through randomized clinical trials. These agents include lithium, other mood stabilizers from the anticonvulsant class, and atypical antipsychotic medications. For children with bipolar mania, however, there are limited data on the safety and efficacy of these pharmacological agents.⁶ Lithium and other mood stabilizers are commonly used for this diagnosis, but the evidence base is not robust for any of these drugs, and except for lithium (for children 12 and older), none of the other mood

stabilizers are FDA approved for this indication.^{4,6} Among the class of atypical antipsychotic medications, risperidone (Risperdal®), aripiprazole (Abilify®), quetiapine (Seroquel®) and olanzapine (Zyprexa®) have been approved for the treatment of pediatric bipolar mania. Although shown to be effective, several of these treatments are associated with adverse events such as movement disorders, weight gain, hyperlipidemia and other metabolic effects, which may limit their usefulness in some patients.⁷ There remains a great need for additional well controlled, randomized, double blind clinical studies to evaluate the efficacy and safety of potential pharmacotherapies in the pediatric population.

1.2.1. Background on Ziprasidone (CP-88,059-1)

Ziprasidone (CP-88,059-1 oral capsule) is an atypical antipsychotic. It has a high affinity for the dopamine D2 receptor, potent in vivo activity in rat models of dopamine antagonism (blocking of d-amphetamine induced locomotor activation and blocking of apomorphine induced stereotypy), and potent activity in an antipsychotic model in rats that is potentially dopamine independent (inhibition of conditioned avoidance). Ziprasidone demonstrates a high 5-HT2A/D2 ratio, which has been associated with a lower risk of extrapyramidal symptoms compared to typical antipsychotics. In addition, blockade of serotonin and norepinephrine re-uptake and 5-HT1A agonist activity may contribute to the alleviation of affective and negative symptoms. Ziprasidone has relatively low affinity for α 1 adrenergic and histamine H1 receptors and muscarinic M1 receptors, which may be associated with modest orthostatic effects and sedation, and low incidence for weight gain and anticholinergic side effects, respectively.⁸ Because ziprasidone is metabolized predominantly by the aldehyde oxidase system, in addition to the cytochrome P450 3A4 (CYP3A4) system, the likelihood of pharmacokinetic interactions between ziprasidone and other drugs is low.⁹

Ziprasidone has been approved by the Food and Drug Administration (FDA) for the treatment of schizophrenia in adults in the United States (approval, February 2001) and in at least 55 other countries. An s-NDA (supplemental New Drug Application) for the treatment of bipolar disorder in adults with manic symptoms was approved by the FDA in August 2004. The safety and efficacy of ziprasidone monotherapy for the treatment of mania in adults was demonstrated in two double blind, placebo controlled trials of 3 weeks duration, and in open label extension trials of up to 104 weeks duration. These studies demonstrated that ziprasidone was superior to placebo in the treatment of subjects with a manic or mixed bipolar episode, with clinically and statistically significant improvement evident as early as Day 2 of treatment. In November 2009, ziprasidone was also approved by the FDA for adult bipolar maintenance treatment based on a 6 month double blind study comparing ziprasidone plus a mood stabilizer vs placebo plus a mood stabilizer in subjects who have been treated and responded for at least 4 months to open label treatment with both agents. The overall profile of adverse events in the adult mania studies is comparable with that seen in schizophrenia studies. Ziprasidone had neutral effects on weight, glucose and lipid profiles in adult patients with mania.⁸

Currently approved and marketed formulations in the US for ziprasidone include the oral capsule (20, 40, 60, and 80 mg) and a rapid onset IM (Intramuscular) injectable form (20 mg/ml). As of October 2017, approximately 2,976,798 patients had been exposed to ziprasidone worldwide, cumulatively (based on prescription data and US unique patient count).

Additional information for this compound may be found in the Single Reference Safety Document (SRSD), which for this study is the Investigator's Brochure.¹⁰

2. STUDY OBJECTIVES AND ENDPOINTS

Primary Objective(s):	Primary Endpoint(s):

 To assess the safety and tolerability of oral ziprasidone (20-80 mg BID) during long term, open label administration in children and adolescents with Bipolar I Disorder who participated in Study A1281198. 	
 Safety Assessments; Adverse event reporting; Clinical laboratory testing; Physical examinations; Blood pressure and pulse; Height and weight; Body Mass Index (BMI) and BMI Z score; Waist circumference; Electrocardiograms, including QTc; Special Safety Assessments; Movement Disorder Scales (SARS, BAS, and AIMS); Columbia Suicide Severity Rating Scale (C-SSRS); Child Depression Rating Scale (CDRS-R); Efficacy Assessments; Young Mania Rating Scale; Clinical Global Impression of Severity (CGI-S); Children's Global Assessment Scale (CGAS).

3. STUDY DESIGN

This 26 week open label extension study is designed to provide information on the safety and tolerability of oral ziprasidone (20 to 80 mg BID with meals) during long term administration in children and adolescents with Bipolar I Disorder (current or most recent episode manic). It will enroll subjects who have participated in the 4 week, double blind, placebo controlled safety and efficacy trial, Study A1281198, meet study entry criteria, and wish to receive treatment with open label ziprasidone.

The number of subjects entering this open-label trial will be determined by the number of subjects electing to continue treatment after completing or withdrawing from the preceding double blind Study A1281198. We estimate that approximately 55 subjects randomized in the double blind study (based on the increased sample size of N=194 subjects) will be eligible to continue in this open label extension. With an expected dropout rate of approximately 35%, this gives an estimate of approximately 40 subjects to complete this 26 week open label study (if all 55 subjects enter the extension study).

The final visit of the double blind trial (Week 4 or early termination visit from A1281198) will serve as the Baseline Visit for the extension study. The first 1-14 days of Study A1281201 will be considered a transition period during which the study drug will continue to be administered under double-blind conditions. During this double-blind transition period, subjects who were on placebo in Study A1281198 will be provided active medication that will allow them to be titrated up to the appropriate weight-adjusted target dose, following titration schedule that was employed in Study A1281198. Subjects who were on active medication (ziprasidone) at the end of Study A1281198 will continue on that treatment course under double-blind conditions. At the end of the double-blind transition period, all subjects will receive open label ziprasidone.

Any subject who cannot tolerate the transition study medication during Week 1 should be discontinued from the study.

After the Week 2 visit for the ≥ 45 kg subjects and after the Week 1 visit for the < 45 kg subjects, dosing will be open label and flexible, with dosing adjustments made at the discretion of the investigator to maintain optimal efficacy and tolerability. For subjects with a body weight of ≥ 45 kg, the target dose range is a total daily dose of 120 mg to 160 mg/day given in two divided doses with food. For subjects with a body weight < 45 kg, the target dose range is a total daily dose of 60 mg to 80 mg/day given in two divided doses with food.

Subjects who cannot tolerate a dose of 80 mg/day will be allowed to have a dose reduction and to continue study treatment at a lower dose that is tolerable to them. The minimum permitted dose is 40 mg/day (20 mg BID) for all subjects.

Post Baseline visits will occur at Weeks 1, 2, 4, 6, 10, 14, 18, 22 and 26 during treatment, with a follow up visit at Week 27.

Contact may occur via telephone and must occur 28 to 35 days from administration of the final dose of investigational product to capture any potential adverse events (see the [Time Period for Collecting AE/SAE Information](#) section) and to confirm appropriate contraception usage (see the [Contraception](#) section).

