During the dose transition period (Weeks 1-2, Days 1-14), subjects will receive a study drug blister card for each week of transition dosing. Subjects weighing ≥ 45 kg will receive 2 weeks of transition medication, while subjects weighing less than < 45 kg will receive 1 week of transition medication.

At the baseline visit of the A1281201 study, subjects will transition onto active medication if previously assigned to the placebo group or continue on active study drug. Over the course of the double-blind dose transition period, subjects < 45 kg will be transitioned to a total daily dose of 60 mg a day by Day 7 of Week 1 and subjects ≥ 45 kg will be transitioned to a total daily dose of 120 mg a day by Day 10 of Week 2. (Subjects on 160 mg, 140 mg, 100 mg, and 80 mg active at the end of Study A1281198 will all be transitioned to 120 mg a day at the end of the two-week transition period. Subjects on 120 mg active at the end of Study A1281198 will remain on 120 mg a day through the dose transition period).

During the dose transition period, investigators, subjects, and the study team will be kept blinded to the content of the dose transition cards (which contain both placebo and active ziprasidone capsules) but not to the dose level of study medication.

Dose level for each day of the transition dosing card for subjects who were on placebo or ziprasidone in Study A1281198 are provided in [Table 1](#), [Table 2](#), [Table 3](#) and [Table 4](#).

Any subject who cannot tolerate the transition study medication during Week 1 should be discontinued from the study.

After the Week 2 visit for the ≥ 45 kg subjects and after the Week 1 visit for the <45 kg subjects, dosing will be open label and flexible, with dosing adjustments made at the discretion of the investigator to maintain optimal efficacy and tolerability. The target dose range for subjects <45 kg is 60 mg to 80 mg/day and for subjects ≥ 45 kg, 120 mg to 160 mg/day, which are identical to the target dose ranges used in Study A1281198.

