4.1. Inclusion Criteria

Subjects must meet all of the following inclusion criteria to be eligible for enrollment into the study:

1. Evidence of personally signed and dated informed consent document by the legal representative and an assent document by the subject indicating that the subject and a legal representative have been informed of all pertinent aspects of the study.
2. Subjects and their legal guardians who are willing and able to comply with scheduled visits, treatment plan, laboratory tests, and other study procedures.
3. The subjects must have received investigational product in Study A1281198 and completed at least 3 weeks of double blind treatment before entering this open label extension. However, subjects who have insufficient treatment response and have reached their maximum tolerated dose may enroll in the open label extension as early as 1 week after the end of their titration.
4. In the investigator's opinion, the subject must be likely to benefit from antipsychotic therapy and must have been free from any clinically significant safety concerns during the preceding double blind study (ie, in the opinion of the investigator, the benefits that the subject is likely to derive from continued participation must outweigh the risks).
5. All fertile male subjects and female subjects of childbearing potential who are sexually active and/or their legal guardians, as appropriate, must agree that a highly effective method of contraception be used as outlined in this protocol and for the duration of the study and for 28 days after the last dose of investigational product.

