8	40	40	80

* Subjects on a dose of 160 mg at the end of the A1281198 study will remain at that dose for 1 additional day during the transition period due to the Day 1 card PM dose design. Starting on Day 2 of the transition period these subjects will receive a total daily dose of 140 mg/day.

120 mg Week 2 Active Titration Card			
Day	AM Dose (mg)	PM Dose (mg)	Total Daily Dose (mg)
1		60	120
2	60	60	120
3	60	60	120
4	60	60	120
5	60	60	120
6	60	60	120
7	60	60	120
8	60	60	120

120 mg Week 2 Placebo Titration Card			
Day	AM Dose (mg)	PM Dose (mg)	Total Daily Dose (mg)
1	40	60	100
2	40	60	100
3	60	60	120
4	60	60	120
5	60	60	120
6	60	60	120
7	60	60	120
8	60	60	120

Table 2. Double-Blind Dose Transition Blister Cards for ≥ 45 kg Subjects on 120 mg/day of Active Ziprasidone or Placebo at End of Study A1281198, Weeks 1 and 2

120 mg Week 1 Active Titration Card			
Day	AM Dose (mg)	PM Dose (mg)	Total Daily Dose (mg)
1		60	120
2	60	60	120
3	60	60	120
4	60	60	120
5	60	60	120
6	60	60	120
7	60	60	120
8	60	60	120

120 mg Week 1 Placebo Titration Card			
Day	AM Dose (mg)	PM Dose (mg)	Total Daily Dose (mg)
1		20	20
2	20	20	40
3	20	20	40
4	20	40	60
5	20	40	60
6	40	40	80
7	40	40	80
8	40	40	80

120 mg Week 2 Active Titration Card			
Day	AM Dose (mg)	PM Dose (mg)	Total Daily Dose (mg)
1	60	60	120
2	60	60	120
3	60	60	120
4	60	60	120
5	60	60	120
6	60	60	120
7	60	60	120
8	60	60	120

120 mg Week 2 Placebo Titration Card			
Day	AM Dose (mg)	PM Dose (mg)	Total Daily Dose (mg)
1	40	60	100
2	40	60	100
3	60	60	120
4	60	60	120
5	60	60	120
6	60	60	120
7	60	60	120
8	60	60	120

Table 3. Double-Blind Dose Transition Blister Cards for ≥ 45 kg Subjects on 80 mg/day or 100 mg of Active Ziprasidone or Placebo at End of Study A1281198, Weeks 1 and 2

100 mg Week 1 Active Titration Card			
Day	AM Dose (mg)	PM Dose (mg)	Total Daily Dose (mg)
1		60	100*
2	40	60	100
3	40	60	100
4	40	60	100
5	40	60	100
6	40	60	100
7	40	60	100
8	40	60	100

100 mg Week 1 Placebo Titration Card			
Day	AM Dose (mg)	PM Dose (mg)	Total Daily Dose (mg)
1		20	20
2	20	20	40
3	20	20	40
4	20	40	60
5	20	40	60
6	40	40	80
7	40	40	80
8	40	40	80

* Subjects who were assigned 80 mg at the end of Study A1281198 will have a 20 mg increase in dose starting on Day 1 of the double blind transition period due to the design of the transition dose card.

120 mg Week 2 Active Titration Card			
Day	AM Dose (mg)	PM Dose (mg)	Total Daily Dose (mg)
1	60	60	120
2	60	60	120
3	60	60	120
4	60	60	120
5	60	60	120
6	60	60	120
7	60	60	120
8	60	60	120

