120 mg Week 2 Placebo Titration Card			
Day	AM Dose (mg)	PM Dose (mg)	Total Daily Dose (mg)
1	40	60	100
2	40	60	100
3	60	60	120
4	60	60	120
5	60	60	120
6	60	60	120
7	60	60	120
8	60	60	120

Table 4. Double Blind Dose Transition Blister Cards for <45 kg Subjects on 40 mg/day, 60 mg/day, or 80 mg of Active Ziprasidone or Placebo at End of Study A1281198, Week 1

60 mg Week 1 Active Titration Card				60 mg Week 1 Placebo Titration Card			
Day	AM Dose (mg)	PM Dose (mg)	Total Daily Dose (mg)	Day	AM Dose (mg)	PM Dose (mg)	Total Daily Dose (mg)
1		40	60/80*	1		20	20
2	20	40	60	2	20	20	40
3	20	40	60	3	20	20	40
4	20	40	60	4	20	20	40
5	20	40	60	5	20	40	60
6	20	40	60	6	20	40	60
7	20	40	60	7	20	40	60
8	20	40	60	8	20	40	60

* Subjects who were assigned 40 mg at the end of Study A1281198 will have a 20 mg increase in dose starting on Day 1 of the double blind transition period due to the design of the transition dose card. Subjects who were assigned 80 mg at the end of Study A1281198 will receive 80 mg on Day 1 of the dose transition week but from Day 2 onwards will receive a total daily dose of 60 mg/day.

Subjects weighing <45 kg should be issued an open label, fixed dosing card with the desired total daily dose for the second week of the dose transition phase(ie, either 40 mg/day, 60 mg/day, or 80 mg/day; see Table 5, [Table 6](#), or [Table 7](#)).

The investigator will decide which fixed dose blister card to provide to the subject for the following week, based on clinical judgment.

Table 5. 40 mg Fixed Dose Regimen

Day	AM Dose (mg)	PM Dose (mg)	Total Daily Dose (mg)
1	20	20	40
2	20	20	40
3	20	20	40
4	20	20	40
5	20	20	40
6	20	20	40
7	20	20	40
8	20	20	40

Table 6. 60 mg Fixed Dose Regimen

Day	AM Dose (mg)	PM Dose (mg)	Total Daily Dose (mg)
1	20	40	60
2	20	40	60
3	20	40	60
4	20	40	60
5	20	40	60
6	20	40	60
7	20	40	60
8	20	40	60

Table 7. 80 mg Fixed Dose Regimen

Day	AM Dose (mg)	PM Dose (mg)	Total Daily Dose (mg)
1	40	40	80
2	40	40	80
3	40	40	80
4	40	40	80
5	40	40	80
6	40	40	80
7	40	40	80
8	40	40	80

Subjects weighing ≥ 45 kg should be issued an open label fixed dosing card with the desired total daily dose at the start of the third week (Day 15) of the extension study (ie, either 80 mg/day, 100 mg/day, 120 mg/day, 140 mg/day or 160 mg/day total daily dose; see Table 8-[Table 11](#)).

Table 8. 100 mg Fixed Dose Regimen

Day	AM Dose (mg)	PM Dose (mg)	Total Daily Dose (mg)
1	40	60	100
2	40	60	100
3	40	60	100
4	40	60	100
5	40	60	100
6	40	60	100
7	40	60	100

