5.5. Administration

As study drug administration is complex, the parent or guardian should closely supervise dosing throughout the study, especially during the transition period. Depending on the assigned investigational product, 1 to 2 capsules are taken in the morning and 1 to 2 capsules in the evening about 12 hours apart. If a dose is missed, the missed dose should be taken as soon as possible, but the AM and PM doses should be separated by a minimum of 4 hours. The missed dose should be skipped if <4 hours remain to the next scheduled dose.

All investigational product is to be taken with food and approximately 12 hours apart. Capsules are to be taken intact. Swallow the capsule whole. Do not crush or chew the capsule.

Transition Period:

The target dose ranges for subjects <45 kg is 60 to 80 mg/day and for subjects ≥ 45 kg, 120 to 160 mg/day, which are identical to the target dose ranges used in Study A1281198.

In general, the target dose should be attained by Days 7-14. For subjects with a body weight ≥ 45 kg, the target dose range is 120 to 160 mg/day. A dose of 160 or 140 mg/day should not be achieved before Day 14 of treatment.

For subjects with a body weight <45 kg, the target dose range is 60-80 mg/day.

Any subject who cannot tolerate the transition study medication during Week 1 should be discontinued from the study.

Open-Label Weeks 3-26

After the Week 2 visit for the ≥ 45 kg subjects and after the Week 1 visit for the <45 kg subjects, dosing will be open-label and flexible, with dosing adjustments made at the discretion of the investigator to maintain optimal efficacy and tolerability. Subjects who cannot tolerate a dose of 80 mg/day will be allowed to have a dose reduction and to continue study treatment at a lower dose that is tolerable to them. The minimum permitted dose is 40 mg/day (ie, 20 mg BID) for all subjects. The site will dispense 2 blister cards to the

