5.6. Summary of the Dose Titration Schedule for Study A1281201

1. No dose adjustments are allowed during Week 1 of the Dose Transition period (for either the <45 kg or ≥ 45 kg dose category); subjects who cannot tolerate the Week 1 dose titration should be withdrawn from the study.
2. Weekly dose adjustments (increases or decreases) are allowed from Week 2 of the Dose Transition period to the end of the study (Week 26). In general, dose adjustments should not occur more frequently than every 7 days to provide an adequate period of time to evaluate the clinical effect of the dose adjustment. Dose adjustments are achieved by issuing an open label fixed dosing card to the subject (ie, with a total daily dose of 40 mg, 60 mg, 80 mg, 100 mg, 120, 140 mg, or 160 mg).
3. The dose may be increased if the subject has been tolerating the current dose level without significant side effects; but, in the clinical judgment of the investigator, has had an insufficient clinical efficacy response. The clinical rationale for the dose increase should be documented in the source documentation for the subject.

4. In general, dose increases should not exceed 20 mg. However, subjects weighing ≥ 45 kg may be increased to 140 mg or 160 mg total daily dose if they have tolerated the 120 mg dose well, have reached Day 15 of the study, and have had an insufficient clinical efficacy response to the 120 mg total daily dose.
5. The dose may be decreased if, in the clinical judgment of the investigator, the subject is not tolerating the current dose well and is likely to benefit from continued treatment with a lower dose of study drug that may be better tolerated. There is no limit on the number of dose decreases; however, subjects who cannot tolerate a minimum total daily dose of 40 mg should be withdrawn from the study. The clinical rationale for the dose decrease should be documented in the source documentation for the subject. In general, dose decreases should not exceed 40 mg.
6. Subjects who, in the clinical judgment of the investigator, have reached their maximum tolerated dose and still have an insufficient clinical response should be withdrawn from the study.

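### For two low-dose groups already on ziprasidone, the blinded Week 1 card forces a 20 mg rise with no adjustment and withdrawal if not tolerated, although their prior dose is one the extension permits

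*Protocol*

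**What the plan says.** **Design statement.** Protocol Section 3, repeated in SAP 2.1, says of prior-ziprasidone subjects: "Subjects who were on active medication (ziprasidone) at the end of Study A1281198 will continue on that treatment course under double-blind conditions".

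**Cards.** The Protocol Summary and Section 5.1 say that ≥45 kg subjects who ended on 160, 140, 100 or 80 mg "will all be transitioned to 120 mg a day at the end of the two-week transition period"; those on 120 mg stay there. Subjects <45 kg go to 60 mg in Week 1. The footnote to Table 3 (≥45 kg) says: "Subjects who were assigned 80 mg at the end of Study A1281198 will have a 20 mg increase in dose starting on Day 1". The footnote to Table 4 (<45 kg) says: "Subjects who were assigned 40 mg at the end of Study A1281198 will have a 20 mg increase in dose starting on Day 1". Both give the design of the card as the reason.

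**Entry.** Inclusion criterion 3 normally requires three weeks of double-blind treatment, with an exception: "subjects who have insufficient treatment response and have reached their maximum tolerated dose may enroll in the open label extension", as early as one week after titration ends.

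**Week 1 rule.** Section 5.6 item 1 allows no dose adjustment in Week 1 in either weight group, and "subjects who cannot tolerate the Week 1 dose titration should be withdrawn from the study".

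**Permitted doses.** Section 5.5 states: "The minimum permitted dose is 40 mg/day (ie, 20 mg BID) for all subjects"; Section 3 has the same minimum. In Section 6.4 the dose-related withdrawal criterion is inability to tolerate 40 mg/day. Section 5.4.2 offers a 40 mg card to <45 kg subjects from the second week, and an 80 mg/day dose to ≥45 kg subjects from Day 15.

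**Reporting.** SAP 6.1 tabulates withdrawals and reasons overall and by treatment group. SAP 6.5.1 summarises adverse events from first open-label dosing to the end of participation. Neither separates the blinded transition from the flexible-dose period.

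**The concern.** Take a ≥45 kg subject who ended the parent study on 80 mg/day because more was not tolerated. The subject is eligible, receives 100 mg/day from Day 1, cannot have it reduced that week, and is withdrawn if it is not tolerated. The same protocol would let this subject take 80 mg/day from Day 15. The <45 kg subject who ended on 40 mg/day is in the same position at 60 mg/day, with 40 mg/day available one week later. No card or exemption is described for a subject whose maximum lies below the card dose.

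Two things are at stake. First, a site that follows the text can move a child above a known maximum tolerated dose, because the entry rule and the dosing rule were not written with each other in view. Second, the only objective is long-term safety and tolerability over 20–80 mg BID. A Week 1 withdrawal from a forced rise enters the same tables as a withdrawal in Month 5 on a flexibly chosen dose, and the planned summaries do not tell them apart.

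**Working it through.** **Inputs.** Card doses come from Tables 1–4 in Protocol Section 5.4.2. The usual AM/PM split at each total dose comes from the fixed-dose card list in Section 5.4.1; that the parent study used the same split is an assumption.

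**Reproducing the footnotes.** The Week 1 active cards supply only a PM dose on Day 1, so the Day 1 total is the prior AM dose plus the card's PM dose.

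- ≥45 kg from 80 mg: 40 + 60 = 100 mg, and 100 − 80 = +20 mg. Agrees with the Table 3 footnote.
- <45 kg from 40 mg: 20 + 40 = 60 mg, and 60 − 40 = +20 mg. Agrees with the Table 4 footnote.

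**All listed active end doses.** Change = card total daily dose − parent-study end dose; percentage = change ÷ end dose. Week 1 is shown from Day 2.

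| Weight | End dose (mg/day) | Week 1 card | Change | Week 2 card | Change from end dose |
|---|---|---|---|---|---|
| ≥45 kg | 160 | 140 | −20 (−12.5%) | 120 | −40 (−25%) |
| ≥45 kg | 140 | 140 | 0 | 120 | −20 (−14.3%) |
| ≥45 kg | 120 | 120 | 0 | 120 | 0 |
| ≥45 kg | 100 | 100 | 0 | 120 | +20 (+20%) |
| ≥45 kg | 80 | 100 | +20 (+25%) | 120 | +40 (+50%) |
| <45 kg | 80 | 60 | −20 (−25%) | none | – |
| <45 kg | 60 | 60 | 0 | none | – |
| <45 kg | 40 | 60 | +20 (+50%) | none | – |

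By the end of the cards, 3 of 8 listed doses are raised, 2 unchanged and 3 lowered. Only 2 of 8 are raised in Week 1, when the no-adjustment and withdrawal rule applies: 80 mg at ≥45 kg and 40 mg at <45 kg.

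**Week 2, ≥45 kg.** The 100 mg group rises only here, and the passages disagree on whether the dose can be changed. Section 5.6 item 2 allows increases and decreases from Week 2 of the transition, by issuing an open-label card, and Section 5.4.2 makes the second transition card conditional on need. Against that, Sections 3 and 5.5 start flexible dosing after the Week 2 visit, and Section 5.4.2 issues the first open-label card on Day 15. The Week 2 figures above are card doses, not settled exposures.

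**Entry against withdrawal.** Inclusion 3 admits subjects with insufficient response at their maximum tolerated dose. Section 5.6 item 6 and the insufficient-response row in Section 6.4 say that subjects in that state should be withdrawn. A ziprasidone subject admitted by that clause can meet a withdrawal criterion on entry.

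**Weight of one withdrawal.** With about 55 expected entrants (Section 9.1), 1 ÷ 55 = 1.8 percentage points. Subjects per end dose are not given, so no expected count can be formed.

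**The case against.** The strongest reply is that the protocol discloses all this and gives sites safeguards. The Section 3 sentence can be read as staying on active drug; the Protocol Summary and Section 5.1 say so and then list the dose changes. Investigators are not blinded to dose level, so they can see the coming card before enrolling a subject. Inclusion 4 requires freedom from clinically significant safety concerns and a favourable benefit–risk judgement, and contact is required between Baseline and Week 1. Inclusion 3 is an early-entry exception for non-responders under blind treatment, some of whom were on placebo.

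Much of that stands. The Section 3 wording alone would be a minor matter. But the safeguards depend on an investigator noticing the conflict; no text says what to do about a subject whose maximum lies below the card. A low maximum tolerated dose is not necessarily a safety concern under Inclusion 4. Responders at a low tolerated dose can also enter by the ordinary three-week route, where the insufficient-response rules do not apply. Nor does blinding alone explain the rise, since the active cards hold the dose in Week 1 for subjects from 60, 100, 120 and 140 mg.

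Stronger readings that a reader might infer, and that the documents do not support:

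- *The transition raises prior-ziprasidone subjects in general.* Five of the eight listed doses are unchanged or lowered.
- *The rise breaks Section 5.6 item 3*, "The dose may be increased if the subject has been tolerating the current dose level without significant side effects". That item plausibly governs adjustments made by the investigator with open-label cards, not a pre-set blinded card.
- *The 40 mg/day minimum already applies in Week 1.* In Section 5.5 it sits under Weeks 3–26, and in Section 3 it follows the flexible-dosing paragraph. It shows that the dose is permitted in the extension, not that a Week 1 reduction is.
- *The cards do produce withdrawals, leaving a selected higher-tolerance group in Weeks 3–26.* Without counts by dose this is possible but not shown; affected subjects could be few or none.

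**Conclusion.** Wrong as written, in narrow form: the rules conflict. For subjects ≥45 kg from 80 mg/day and <45 kg from 40 mg/day, the card forces a 20 mg rise from Day 1 (+25% and +50%), with no adjustment in Week 1 and withdrawal if it is not tolerated, although the prior dose is available later in the same study. For ≥45 kg subjects from 100 mg/day the rise (+20%) comes only in Week 2, where the text contradicts itself on adjustment. Inclusion 3 separately conflicts with Section 5.6 item 6 and Section 6.4.

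This can produce withdrawals that reflect the card rather than long-term intolerance; their number cannot be computed from the documents. The conclusion assumes that some subjects in these two groups ended the parent study at their maximum tolerated dose, which Inclusion 3 makes possible but does not quantify. It should be fixed, but it does not undermine the study as a whole.

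**What to change.** **Protocol.** The sponsor should reconcile Inclusion 3, Tables 3 and 4 with their footnotes, Section 5.6 items 1, 2 and 6, the 40 mg/day minimum, the Section 6.4 withdrawal criteria, and the sentence shared by Section 3 and SAP 2.1. A subject entering at a maximum tolerated dose should fall under one consistent rule. The clinical team decides which; no dose or rule is proposed here. The Week 2 conflict for ≥45 kg subjects should be settled in the same amendment.

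**SAP 6.1 and 6.5.1.** Tabulate withdrawals and adverse events separately for the blinded transition (Weeks 1–2, or Week 1 if <45 kg) and the flexible-dose period. Because 6.5.1 counts events from first open-label dosing while the transition is double-blind, state explicitly that transition events are included. Within Ziprasidone/Ziprasidone only, split further by whether the card raised, kept or lowered the parent-study end dose. The split has no meaning for Placebo/Ziprasidone, where every card starts at 20 mg.

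**Cost.** A wording amendment and one extra split of existing tables. No new data are needed, since the parent end dose determines the card. The drawback is small cells in a descriptive table, so counts will say more than percentages.
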